4. STUDY OBJECTIVES

4.1 Primary Objective

To evaluate the relative bioavailability of a single 80 mg subcutaneous (SC) dose of ixekizumab Test Formulation 1 and Test Formulation 2 compared to the commercial formulation (Reference).

4.2 Secondary Objective

To evaluate the safety and tolerability of a single 80 mg SC dose of ixekizumab Test Formulation 1 and Test Formulation 2 compared to the commercial formulation (Reference).

4.3 Exploratory Objective

To evaluate the effect of ixekizumab on immunogenicity.

5. STUDY DESIGN

Study I1F-MC-RHCT is a Phase 1, subject-blind, 3-arm, randomized, parallel-design study in healthy subjects.

Eligible subjects will be admitted to the clinical research unit (CRU) on Day -1 and randomized 1:1:1 to 1 of 3 possible treatments. On Day 1, subjects will receive a single SC dose of one of the following treatments, according to the randomization schedule:

- 80 mg ixekizumab Commercial Formulation (Reference)
- 80 mg ixekizumab Test Formulation 1
- 80 mg ixekizumab Test Formulation 2

Subjects may be allowed to leave the CRU after completing the 4-hour safety assessments on Day 1, at the investigator's discretion, and will return for PK and immunogenicity sampling and safety assessments at predefined times up to 12 weeks postdose.

[figure not shown]
6. TREATMENTS

The following is a list of the study treatment abbreviations that will be used in the TFLs.

Study Treatment Name	Abbreviation	Treatment order in TFL
80 mg ixekizumab Commercial Formulation (Reference)	Reference	1
80 mg ixekizumab Test Formulation 1	Test Formulation 1	2
80 mg ixekizumab Test Formulation 2	Test Formulation 2	3

7. SAMPLE SIZE JUSTIFICATION

Up to 99 subjects may be enrolled to ensure that 78 subjects (26 for each treatment) complete the study.

Subjects who are randomized but not administered treatment may be replaced to ensure that 78 subjects (26 for each treatment) complete the study.

8. DEFINITION OF ANALYSIS POPULATIONS

The "Safety" population will consist of all enrolled subjects, whether or not they completed all protocol requirements.

The "Pharmacokinetic" population will consist of all subjects who received one dose of ixekizumab and have evaluable PK data.

All protocol deviations and adverse events (AEs) that occur during the study will be considered for their severity/impact and will be taken into consideration when subjects are assigned to analysis populations.

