Appendix 1. Abbreviations and Definitions

Term	Definition
ADA	antidrug antibodies
AE	adverse event: Any untoward medical occurrence in a patient or clinical investigation subject administered a pharmaceutical product that does not necessarily have a causal relationship with this treatment. An AE can therefore be any unfavorable and unintended sign (including an abnormal laboratory finding), symptom, or disease temporally associated with the use of a medicinal (investigational) product, whether or not related to the medicinal (investigational) product.
AI	autoinjector
ALP	alkaline phosphatase
ALT	alanine aminotransferase
AST	aspartate aminotransferase
AUC(0-∞)	area under the concentration versus time curve from zero to infinity
AUC(0-t_{last})	area under the concentration versus time curve from time zero to time t, where t is last the time point with a measurable concentration
BCG	Bacillus Calmette-Guérin
BMI	body mass index
CEC	Clinical Events Committee
CI	confidence interval
C_{max}	maximum drug concentration
complaint	A complaint is any written, electronic, or oral communication that alleges deficiencies related to the identity, quality, purity, durability, reliability, safety or effectiveness, or performance of a drug or drug delivery system.
compliance	Adherence to all the study-related requirements, good clinical practice (GCP) requirements, and the applicable regulatory requirements.
confirmation	A process used to confirm that laboratory test results meet the quality requirements defined by the laboratory generating the data and that Lilly is confident that results are accurate. Confirmation will either occur immediately after initial testing or will require that samples be held to be retested at some defined time point, depending on the steps required to obtain confirmed results.
CP	Clinical Pharmacologist
CRP	Clinical Research Physician: Individual responsible for the medical conduct of the study. Responsibilities of the CRP may be performed by a physician, clinical research scientist, global safety physician or other medical officer.
CRU	clinical research unit

C-SSRS	Columbia Suicide Severity Rating Scale
ECG	electrocardiogram
eCRF	electronic case report form
enroll	The act of assigning a subject to a treatment. Subjects who are enrolled in the study are those who have been assigned to a treatment.
enter	Subjects entered into a study are those who sign the informed consent form directly or through their legally acceptable representatives.

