9. STATISTICAL METHODOLOGY

9.1 General

Data listings will be provided for all data that are databased. Summary statistics and statistical analysis will only be presented for data where detailed in this SAP. For continuous data, summary statistics will include the arithmetic mean, arithmetic standard deviation (SD), median, min, max and N; for log-normal data (e.g. the PK parameters: area under the concentration time curve [AUC] and maximum observed drug concentration [C_{max}]) the geometric mean and geometric coefficient of variation (CV%) will also be presented. For categorical data, frequency count and percentages will be presented. Data listings will be provided for all subjects up to the point of withdrawal, with any subjects excluded from the relevant population highlighted. Summary statistics and statistical analyses will generally only be performed for subjects included in the relevant analysis population. For the calculation of summary statistics and statistical analysis, unrounded data will be used.

Mean change from baseline is the mean of all individual subjects' change from baseline values. Each individual change from baseline will be calculated by subtracting the individual subject's baseline value from the value at the time point. The individual subject's change from baseline values will be used to calculate the mean change from baseline using a SAS procedure such as Proc Univariate.

Data analysis will be performed using SAS[®] Version 9.4 or greater.

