9.4 Safety and Tolerability Assessments

9.4.1 Adverse events

Where changes in severity are recorded in the Case Report Form (CRF), each separate severity of the AE will be reported in the listings, only the most severe will be used in the summary tables. A pre-existing condition is defined as an AE that starts before the subject has provided written informed consent and is ongoing at consent. A non-treatment emergent AE is defined as an AE which starts after informed consent but prior to dosing. A treatment-emergent AE is defined as an AE which occurs postdose or which is present prior to dosing and becomes more severe postdose.

All AEs will be listed. Treatment-emergent AEs will be summarized by treatment and severity. The frequency (the number of AEs, the number of subjects experiencing an AE and the percentage of subjects experiencing an AE) of treatment-emergent AEs will be summarized by treatment, Medical Dictionary for Regulatory Activities (MedDRA) version 21.0 system organ class and preferred term. The summary and frequency AE tables will be presented for all causalities. Any serious AEs will be listed.

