9.4.11 Safety and Tolerability Statistical Methodology

Inferential statistical analyses is planned for the pain VAS score, using a mixed repeated measures model.

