14. DATA PRESENTATION

14.1 Derived Parameters

Individual derived parameters (e.g. PK parameters) and appropriate summary statistics will be reported to three significant figures. Observed concentration data, e.g. C_{\max} , should be reported as received. Observed time data, e.g. t_{\max} , should be reported as received. N and percentage values should be reported as whole numbers. Median values should be treated as an observed parameter and reported to the same number of decimal places as minimum and maximum values.

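### The SAP's all-enrolled Safety population puts randomized-but-undosed subjects in the TEAE denominator, although they cannot have a TEAE (minor)

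*SAP*

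**What the plan says.** - **Safety population.** SAP Section 8 states that the Safety "population will consist of all enrolled subjects, whether or not they completed all protocol requirements". Protocol Section 10.3 has the same rule. Neither adds a dosing condition, although the pharmacokinetic population in SAP Section 8 does require a dose.
- **Meaning of enrolled.** Protocol Appendix 1: "Subjects who are enrolled in the study are those who have been assigned to a treatment".
- **Undosed subjects are foreseen.** SAP Section 7 (and protocol Section 10.1): "Subjects who are randomized but not administered treatment may be replaced". Neither place says that the replaced subject leaves the Safety population.
- **TEAE definition.** SAP Section 9.4.1: "A treatment-emergent AE is defined as an AE which occurs postdose or which is present prior to dosing and becomes more severe postdose".
- **What is reported.** Among the frequencies in SAP Section 9.4.1, "the percentage of subjects experiencing an AE) of treatment-emergent AEs will be summarized by treatment". That section names no denominator.
- **Default set for summaries.** SAP Section 9.1: "Summary statistics and statistical analyses will generally only be performed for subjects included in the relevant analysis population".
- **Precision and inference.** SAP Section 14.1: "N and percentage values should be reported as whole numbers". SAP Section 9.4.11: "Inferential statistical analyses is planned for the pain VAS score"; no other safety variable has planned inference.

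**The concern.** A subject who is randomized and then not dosed meets the SAP's definition of the Safety population, but cannot meet either limb of its TEAE definition, since both refer to what happens after dosing. Such a subject can only leave an arm's TEAE percentage unchanged (if it is zero) or lower it.

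TEAEs are a named secondary endpoint, compared between each test formulation and the reference. If the number of undosed subjects differs by arm, part of any difference in TEAE percentages comes from the denominator and not from the formulation. An all-enrolled denominator is sometimes thought cautious; for an event that requires exposure it works the other way and makes the product look slightly better tolerated.

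**Working it through.** The plan states no figure here: it gives neither an expected number of undosed subjects nor a TEAE rate. The check therefore follows the definitions and then sizes the effect under stated assumptions.

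**Definitions**

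1. Randomized means assigned to a treatment, which means enrolled (protocol Appendix 1).
2. Enrolled means in the Safety population (SAP Section 8).
3. No dose means no postdose onset and no postdose worsening, hence no TEAE (SAP Section 9.4.1).
4. The TEAE percentage is taken over the relevant population (SAP Section 9.1), by implication Safety.

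**Inputs**

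- From the documents: 26 completers per arm; up to 99 enrolled at 1:1:1, so 99/3 = 33 per arm; percentages printed as whole numbers.
- Assumed: u = 1 or 2 undosed subjects per arm; D = 26 dosed, the completer target; several counts r of subjects with a TEAE.

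**Scaling factor**

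Reported percentage = 100 × r/(D + u). Percentage among dosed subjects = 100 × r/D. The ratio is D/(D + u).

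- 26 dosed: u = 1 gives 26/27 = 0.963; u = 2 gives 26/28 = 0.929.
- 33 randomized: u = 1 gives 32/33 = 0.970; u = 2 gives 31/33 = 0.939.

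**Effect on the printed percentage, 26 dosed**

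| Subjects with a TEAE | Over 26 | Over 27 (u = 1) | Over 28 (u = 2) | Prints as |
|---|---|---|---|---|
| 3 | 11.54 | 11.11 | 10.71 | 12, 11, 11 |
| 8 | 30.77 | 29.63 | 28.57 | 31, 30, 29 |
| 13 | 50.00 | 48.15 | 46.43 | 50, 48, 46 |

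Over all counts from 0 to 26:

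- With u = 1 the printed value falls by 0 to 4 points. The maximum occurs at 22 and 26 of 26; there is no change at 0, 1, 4 or 5.
- With u = 2 it falls by 0 to 7 points. The maximum occurs at 25 and 26 of 26; there is no change at 0 or 1.

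**Unequal arms.** If two arms each have 13 of 26 dosed subjects with a TEAE, and one arm also has 2 undosed subjects, the table shows 50% against 46%: 50.00 − 46.43 = 3.57 points from the denominator alone.

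**Scale.** One subject in an arm of 26 is 100/26 = 3.8 points. At an assumed TEAE rate of 30%, the standard error of a difference between two such arms is 100 × √(2 × 0.3 × 0.7/26) = 12.7 points. The artefact is well inside sampling error.

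**The case against.** The best case on the other side has four parts.

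- **The SAP leaves room to exclude undosed subjects.** The last sentence of Section 8 says protocol deviations and adverse events are weighed when subjects are assigned to populations, and Section 9.1 applies the population rule only generally. This is true, but both are discretionary and neither sets a rule for undosed subjects. The denominator would be settled case by case.
- **The denominator is inferred.** Section 9.4.1 names no population. Summarizing by treatment could mean treatment received, in which case an undosed subject belongs to no column. The table shells mentioned in SAP Section 3 are not available and could also set a dosed-only denominator. Either would remove the problem, but nothing in the visible text says so.
- **The harm is limited.** The same tables give the number of events and the number of subjects with an event, which undosed subjects do not change. Disposition is listed, so a reader could recompute the percentages. This stands, and it is a reason to rate the point minor.
- **Undosed subjects should be rare.** Treatment is one injection given by site staff, and the Schedule of Activities puts randomization on Day 1, the dosing day. This also stands. Still, both documents provide for the case, so the analysis rule should too.

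It can also be said that 26 is a floor for dosed subjects if the completer target is met, so examples based on 26 lean slightly high. The factors for 33 randomized (0.97 and 0.94) show how little this matters.

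**Conclusion.** The concern holds, as a minor point. As written, SAP Section 8 counts randomized-but-undosed subjects in the TEAE denominator by default, and SAP Section 9.4.1 keeps them out of the numerator.

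With an assumed 1 or 2 undosed subjects per arm, non-zero TEAE percentages are scaled by about 0.93 to 0.97. At 8 of 26 that is 1 or 2 printed points. If every randomized subject is dosed, the effect is nil. The size rests on assumed undosed and TEAE counts, and the conclusion on the tables using the Section 8 set.

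No study conclusion is at risk. The TEAE tables are descriptive, the pharmacokinetic population already requires a dose, and neither the SAE listings nor the model for pain on the visual analog scale depends on this denominator.

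**What to change.** In SAP Section 8, define the Safety population, or at least the denominator for TEAE percentages, as randomized subjects who received ixekizumab. Apply the same denominator to other postdose safety percentages, since Sections 9.4.7 (injection-site assessments) and 9.4.10 (immunogenicity) also tabulate frequencies without stating a dosed-only base.

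Keep an all-enrolled set for listings, and list adverse events in randomized-but-undosed subjects separately. No data are then lost, and the protocol Section 10.3.1.1 commitment to list protocol-procedure events is still met.

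Record the change in SAP Section 12, which at present reports none. Aligning protocol Section 10.3 is optional, because SAP Section 3 gives the SAP precedence over the protocol's statistical considerations. If the table shells already use a dosed-only denominator, Section 8 should say so.

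The cost is one sentence in Section 8 and one entry in Section 12. Reported TEAE percentages may look slightly less favourable.

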9. STATISTICAL METHODOLOGY

9.1 General

Data listings will be provided for all data that are databased. Summary statistics and statistical analysis will only be presented for data where detailed in this SAP. For continuous data, summary statistics will include the arithmetic mean, arithmetic standard deviation (SD), median, min, max and N; for log-normal data (e.g. the PK parameters: area under the concentration time curve [AUC] and maximum observed drug concentration [C_{max}]) the geometric mean and geometric coefficient of variation (CV%) will also be presented. For categorical data, frequency count and percentages will be presented. Data listings will be provided for all subjects up to the point of withdrawal, with any subjects excluded from the relevant population highlighted. Summary statistics and statistical analyses will generally only be performed for subjects included in the relevant analysis population. For the calculation of summary statistics and statistical analysis, unrounded data will be used.

Mean change from baseline is the mean of all individual subjects' change from baseline values. Each individual change from baseline will be calculated by subtracting the individual subject's baseline value from the value at the time point. The individual subject's change from baseline values will be used to calculate the mean change from baseline using a SAS procedure such as Proc Univariate.

Data analysis will be performed using SAS[®] Version 9.4 or greater.

9.2 Demographics and Subject Disposition

Subject disposition will be listed. The demographic variables age, sex, race, ethnicity, country of enrolment, site ID, body weight, height and body mass index will be summarized and listed. All other demographic variables will be listed if applicable.

9.3 Pharmacokinetic Assessment

9.3.1 Pharmacokinetic Analysis

The PK parameter estimates will be determined using non-compartmental methods in validated software program, Phoenix WinNonlin (Certara, Version 6.4 or later):

Serum concentrations of ixekizumab and will be used to determine the following PK parameters, when possible:

Parameter	Units	Definition
AUC(0-∞)	ug.day/mL	area under the concentration versus time curve from time zero to infinity
AUC(0-t _{last})	ug.day/mL	area under the concentration versus time curve from time zero to time t, where t is the last time point with a measurable concentration
%AUC(t _{last} -∞)	%	percentage of AUC that is due to extrapolation from the last measurable concentration to infinity
C _{max}	ug/mL	maximum observed drug concentration
t _{max}	day	time of maximum observed drug concentration
t _{1/2}	day	half-life associated with the terminal rate constant (λ_z) in non-compartmental analysis
CL/F	L/h	apparent total body clearance of drug calculated after extra-vascular administration
V _{ss} /F	L	apparent volume of distribution at steady state after extra-vascular administration
V _z /F	L	apparent volume of distribution during the terminal phase after extra-vascular administration

Weight normalized PK parameters will be calculated. Additional PK parameters may be calculated where appropriate.

Any exceptions or special handling of data will be clearly documented within the final study report.

PK analysis will, where possible, be carried out using actual postdose times recorded in the raw data.

Formatting of tables, figures and abbreviations will follow the Eli Lilly Global PK/PD/TS Tool: NON-COMPARTMENTAL PHARMACOKINETIC STYLE GUIDE. The version of the tool effective at the time of PK analysis will be followed.

General PK Parameter Rules

- Actual sampling times will be used in the final analyses of individual PK parameters, except for non-bolus pre-dose sampling times which will be set to zero.
- C_{max} and t_{max} will be reported from observed values. If C_{max} occurs at more than one time point, t_{max} will be assigned to the first occurrence of C_{max}.
- AUC parameters will be calculated using a combination of the linear and logarithmic trapezoidal methods (linear-log trapezoidal rule). The linear trapezoidal method will be applied up to t_{max} and then the logarithmic trapezoidal method will be used after t_{max}. The

minimum requirement for the calculation of AUC will be the inclusion of at least three consecutive serum concentrations above the lower limit of quantification (LLOQ), with at least one of these concentrations following C_{max} .

- AUC(0- ∞) values where the percentage of the total area extrapolated is more than 20% will be flagged. Any AUC(0- ∞) value excluded from summary statistics will be noted in the footnote of the summary table. If AUC(0- ∞) cannot be determined for all subjects an alternative AUC measure, such as AUC to a fixed time point, may be used in the assessment exposure between dose groups.
- Half-life ($t_{1/2}$) will be calculated, when appropriate, based on the apparent terminal log-linear portion of the concentration-time curve. The start of the terminal elimination phase for each subject will be defined by visual inspection and generally will be the first point at which there is no systematic deviation from the log-linear decline in serum concentrations. Half-life will only be calculated when a reliable estimate for this parameter can be obtained comprising of at least 3 data points. If $t_{1/2}$ is estimated over a time window of less than 2 half-lives, the values will be flagged in the data listings. Any $t_{1/2}$ value excluded from summary statistics will be documented in the footnote of the summary table.
- A uniform weighting scheme will be used in the regression analysis of the terminal log-linear portion of the concentration-time curve.
- The parameters based on the last observed quantifiable drug concentration (C_{last}) will be reported.

Individual PK Parameter Rules

- Only quantifiable concentrations will be used to calculate PK parameters with the exception of special handling of certain concentrations reported below the lower limit of quantitation (BQL). Serum concentrations reported as BQL will be set to a value of zero when all of the following conditions are met:
 - The compound is non-endogenous.
 - The samples are from the initial dose period for a subject.
 - The time points occur before the first quantifiable concentration.
- All other BQL concentrations that do not meet the above criteria will be set to missing.
- Also, where two or more consecutive concentrations are BQL towards the end of a profile, the profile will be deemed to have terminated and therefore any further quantifiable concentrations will be set to missing for the calculation of the PK parameters unless it is considered to be a true characteristic of the profile of the drug.

Individual Concentration vs. Time Profiles

- Individual concentrations will be plotted utilizing actual sampling times.
- The terminal point selections will be indicated on a semi-logarithmic plot.

Average Concentration vs. Time Profiles

- The average concentration profiles will be graphed using scheduled (nominal) sampling times.
- The average concentration profiles will be graphed using arithmetic average concentrations.
- The pre-dose average concentration for single-dose data from non-endogenous compounds will be set to zero. Otherwise, only quantifiable concentrations will be used to calculate average concentrations.
- Concentrations at a sampling time exceeding the sampling time window specified in the protocol, or $\pm 10\%$, will be excluded from the average concentration profiles.
- Concentrations excluded from the mean calculation will be documented in the final study report.
- A concentration average will be plotted for a given sampling time only if $2/3$ of the individual data at the time point have quantifiable measurements that are within the sampling time window specified in the protocol or $\pm 10\%$. An average concentration estimated with less than $2/3$ but more than 3 data points may be displayed on the mean concentration plot if determined to be appropriate and will be documented within the final study report.

Treatment of Outliers during Pharmacokinetic Analysis

Application of this procedure to all PK analyses is not a requirement. Rather, this procedure provides justification for exclusion of data when scientifically appropriate. This procedure describes the methodology for identifying an individual value as an outlier for potential exclusion, but does not require that the value be excluded from analysis. The following methodology will not be used to exclude complete profiles from analysis.

Data within an Individual Profile

A value within an individual profile may be excluded from analysis if any of the following criteria are met:

- For PK profiles during single dosing of non-endogenous compounds, the concentration in a pre-dose sample is quantifiable.
- For any questionable datum that does not satisfy the above criteria, the profile will be evaluated and results reported with and without the suspected datum.

Data between Individual Profiles

1. If $n < 6$, then the dataset is too small to conduct a reliable range test. Data will be analyzed with and without the atypical value, and both sets of results will be reported.
2. If $n \geq 6$, then an objective outlier test will be used to compare the atypical value to other values included in that calculation:
 - a. Transform all values in the calculation to the logarithmic domain.
 - b. Find the most extreme value from the arithmetic mean of the log transformed values and exclude that value from the dataset.
 - c. Calculate the lower and upper bounds of the range defined by the arithmetic mean $\pm 3 \times SD$ of the remaining log-transformed values.
 - d. If the extreme value is within the range of arithmetic mean $\pm 3 \times SD$, then it is not an outlier and will be retained in the dataset.
 - e. If the extreme value is outside the range of arithmetic mean $\pm 3 \times SD$, then it is an outlier and will be excluded from analysis.

If the remaining dataset contains another atypical datum suspected to be an outlier and $n \geq 6$ following the exclusion, then repeat step 2 above. This evaluation may be repeated as many times as necessary, excluding only one suspected outlier in each iteration, until all data remaining in the dataset fall within the range of arithmetic mean $\pm 3 \times SD$ of the log-transformed values.

Reporting of Excluded Values

Individual values excluded as outliers will be documented in the final report. Approval of the final report will connote approval of the exclusion.

